7.5.2.5. Visit 5 (Week 8 (D57±3))

- Perform the following assessments: (all ophthalmic procedures to be performed OU)
 - Query for AEs
 - Update medical history and medications
 - Vital signs
 - BCVA (ETDRS)
 - M-CHARTS™
 - Slit-lamp biomicroscopy
 - IOP
 - Indirect ophthalmoscopy
 - SD-OCT
 - SS-OCT angiography (for selected sites)
- **Perform Lucentis® administration** as per drug labeling, and then perform the following procedures after Lucentis® administration.
 - IOP will be measured at 40 (± 10) minutes post-injection.
 - If post-injection IOP is ≤ 21 mmHg AND increased < 10 mmHg from pre-injection IOP and there is no concern regarding retinal artery perfusion, DE-122 or Sham IVT will be administered.
 - If post-injection IOP is > 21 mmHg OR increased ≥ 10 mmHg from pre-injection IOP, IOP measurement will be repeated at 60 (± 10) minutes post-injection.
 - IOP will be measured at 60 (± 10) minutes post-injection, if applicable.
 - If post-injection IOP at 60 (± 10) minutes is ≤ 21 mmHg AND increased < 10 mmHg from pre-injection IOP and there is no concern regarding retinal artery perfusion, DE-122 or Sham IVT will be administered.
 - If post-injection IOP at 60 (± 10) minutes is > 21 mmHg, however the IOP is < 30 mmHg AND increased < 10 mmHg from pre-injection IOP and there is no concern regarding retinal artery perfusion, DE-122 or Sham IVT will be administered per the Clinical Investigator's discretion.
If the Clinical Investigator determine that DE-122 or Sham IVT will Not be administered, the subject will be treated according to the Clinical Investigator's discretion.
 - **If post-injection IOP at 60 (± 10) minutes is ≥ 30 mmHg OR increased ≥ 10 mmHg from pre-injection IOP, DE-122 or Sham IVT should not be administered.** The subject should be prescribed a topical IOP-lowering medication until he or she returns for follow-up per the Clinical Investigator's discretion.

discretion (an unscheduled visit may apply), and the event will be reported as an AE.

- **Perform DE-122 or Sham administration**, and then perform the following procedures after DE-122 or Sham administration.
- After DE-122 or Sham administration, the following will be performed: (all ophthalmic procedures to be performed OU)
 - Within 30 minutes following DE-122 or Sham IVT
 - Slit-lamp biomicroscopy
 - Indirect ophthalmoscopy
 - IOP measurement 40 (± 10) minutes following DE-122 or Sham IVT injection
 - If post-DE-122 or Sham injection IOP is > 21 mmHg OR increased ≥ 10 mmHg from pre-Lucentis[®] injection, IOP measurement will be repeated at 60 (± 10) minutes post-injection.
 - IOP will be measured at 60 (± 10) minutes following DE-122 or Sham IVT injection, if applicable.
 - If post-DE-122 or Sham injection IOP at 60 (± 10) minutes is ≥ 30 mmHg OR increased ≥ 10 mmHg from pre-Lucentis[®] injection IOP, the subject should be prescribed a topical IOP-lowering medication, and the IOP elevation will be reported as an AE. Per the Clinical Investigator's discretion, the subject can return for follow-up (an unscheduled visit may apply).
 - If post-DE-122 or Sham injection IOP at 60 (± 10) minutes is > 21 mmHg AND < 30 mmHg, the subject will be treated according to the Clinical Investigator's discretion.
- AE assessments must be performed after each IVT injection.
- Upload collected images (SD-OCT) of the study eye to the central reading center.
- Schedule the subject to return for Visit 6 (Week 12 (D85 ± 4)). Remind subjects to fast 8 hours prior to next visit.

7.5.2.6. Visit 6 (Week 12 (D85 ± 4))

- Perform the following assessments: (all ophthalmic procedures to be performed OU)
 - Query for AEs
 - Update medical history and medications
 - Vital signs
 - BCVA (ETDRS)
 - M-CHARTSTM
 - Slit-lamp biomicroscopy

- IOP
- Indirect ophthalmoscopy
- SD-OCT
- SS-OCT angiography (for selected sites)
- Fundus photography
- Fluorescein angiography
- Collect urine and blood specimen for the following examinations:
 - Urinalysis
 - Hematology, chemistry serum sample
- **Perform Lucentis® administration** as per drug labeling, and then perform the following procedures after Lucentis® administration.
 - IOP will be measured at 40 (± 10) minutes post-injection.
 - If post-injection IOP is ≤ 21 mmHg AND increased < 10 mmHg from pre-injection IOP and there is no concern regarding retinal artery perfusion, DE-122 or Sham IVT will be administered.
 - If post-injection IOP is > 21 mmHg OR increased ≥ 10 mmHg from pre-injection IOP, IOP measurement will be repeated at 60 (± 10) minutes post-injection.
 - IOP will be measured at 60 (± 10) minutes post-injection, if applicable.
 - If post-injection IOP at 60 (± 10) minutes is ≤ 21 mmHg AND increased < 10 mmHg from pre-injection IOP and there is no concern regarding retinal artery perfusion, DE-122 or Sham IVT will be administered.
 - If post-injection IOP at 60 (± 10) minutes is > 21 mmHg, however the IOP is < 30 mmHg AND increased < 10 mmHg from pre-injection IOP and there is no concern regarding retinal artery perfusion, DE-122 or Sham IVT will be administered per the Clinical Investigator's discretion.
If the Clinical Investigator determine that DE-122 or Sham IVT will Not be administered, the subject will be treated according to the Clinical Investigator's discretion.
 - **If post-injection IOP at 60 (± 10) minutes is ≥ 30 mmHg OR increased ≥ 10 mmHg from pre-injection IOP, DE-122 or Sham IVT should not be administered.** The subject should be prescribed a topical IOP-lowering medication until he or she returns for follow-up per the Clinical Investigator's discretion (an unscheduled visit may apply), and the event will be reported as an AE.
- **Perform DE-122 or Sham administration**, and then perform the following procedures after DE-122 or Sham administration.

- After DE-122 or Sham administration, the following will be performed: (all ophthalmic procedures to be performed OU).
 - Within 30 minutes following DE-122 or Sham IVT
 - Slit-lamp biomicroscopy
 - Indirect ophthalmoscopy
 - IOP measurement 40 (± 10) minutes following DE-122 or Sham IVT injection
 - If post-DE-122 or Sham injection IOP is > 21 mmHg OR increased ≥ 10 mmHg from pre-Lucentis[®] injection, IOP measurement will be repeated at 60 (± 10) minutes post-injection.
 - IOP will be measured at 60 (± 10) minutes following DE-122 or Sham IVT injection, if applicable.
 - If post-DE-122 or Sham injection IOP at 60 (± 10) minutes is ≥ 30 mmHg OR increased ≥ 10 mmHg from pre-Lucentis[®] injection IOP, the subject should be prescribed a topical IOP-lowering medication, and the IOP elevation will be reported as an AE. Per the Clinical Investigator's discretion, the subject can return for follow-up (an unscheduled visit may apply).
 - If post-DE-122 or Sham injection IOP at 60 (± 10) minutes is > 21 mmHg AND < 30 mmHg, the subject will be treated according to the Clinical Investigator's discretion.
- AE assessments must be performed after each IVT injection.
- If subject has not been fasting, schedule the subject as soon as possible for fasting blood draw and urine specimen.
- Upload collected images (Fluorescein angiography, Fundus photography and SD-OCT) of the study eye to the central reading center.
- Schedule the subject to return for Visit 7 (Week 16 (D113 ± 4)).

7.5.2.7. Visit 7 (Week 16 (D113 ± 4))

- Perform the following assessments: (all ophthalmic procedures to be performed OU)
 - Query for AEs
 - Update medical history and medications
 - Vital signs
 - BCVA (ETDRS)
 - M-CHARTS™
 - Slit-lamp biomicroscopy
 - IOP
 - Indirect ophthalmoscopy

- SD-OCT
- SS-OCT angiography (for selected sites)
- **Perform Lucentis® administration** as per drug labeling, and then perform the following procedures after Lucentis® administration.
 - IOP will be measured at 40 (± 10) minutes post-injection.
 - If post-injection IOP is ≤ 21 mmHg AND increased < 10 mmHg from pre-injection IOP and there is no concern regarding retinal artery perfusion, DE-122 or Sham IVT will be administered.
 - If post-injection IOP is > 21 mmHg OR increased ≥ 10 mmHg from pre-injection IOP, IOP measurement will be repeated at 60 (± 10) minutes post-injection.
 - IOP will be measured at 60 (± 10) minutes post-injection, if applicable.
 - If post-injection IOP at 60 (± 10) minutes is ≤ 21 mmHg AND increased < 10 mmHg from pre-injection IOP and there is no concern regarding retinal artery perfusion, DE-122 or Sham IVT will be administered.
 - If post-injection IOP at 60 (± 10) minutes is > 21 mmHg, however the IOP is < 30 mmHg AND increased < 10 mmHg from pre-injection IOP and there is no concern regarding retinal artery perfusion, DE-122 or Sham IVT will be administered per the Clinical Investigator's discretion.
If the Clinical Investigator determine that DE-122 or Sham IVT will Not be administered, the subject will be treated according to the Clinical Investigator's discretion.
 - **If post-injection IOP at 60 (± 10) minutes is ≥ 30 mmHg OR increased ≥ 10 mmHg from pre-injection IOP, DE-122 or Sham IVT should not be administered.** The subject should be prescribed a topical IOP-lowering medication until he or she returns for follow-up per the Clinical Investigator's discretion (an unscheduled visit may apply), and the event will be reported as an AE.
- **Perform DE-122 or Sham administration**, and then perform the following procedures after DE-122 or Sham administration.
- After DE-122 or Sham administration, the following will be performed: (all ophthalmic procedures to be performed OU).
 - Within 30 minutes following DE-122 or Sham IVT
 - Slit-lamp biomicroscopy
 - Indirect ophthalmoscopy
 - IOP measurement 40 (± 10) minutes following DE-122 or Sham IVT injection
 - If post-DE-122 or Sham injection IOP is > 21 mmHg OR increased ≥ 10 mmHg from pre-Lucentis® injection, IOP measurement will be repeated at 60 (± 10) minutes post-injection.

- IOP will be measured at 60 (± 10) minutes following DE-122 or Sham IVT injection, if applicable.
 - If post-DE-122 or Sham injection IOP at 60 (± 10) minutes is ≥ 30 mmHg OR increased ≥ 10 mmHg from pre-Lucentis® injection IOP, the subject should be prescribed a topical IOP-lowering medication, and the IOP elevation will be reported as an AE. Per the Clinical Investigator's discretion, the subject can return for follow-up (an unscheduled visit may apply).
 - If post-DE-122 or Sham injection IOP at 60 (± 10) minutes is > 21 mmHg AND < 30 mmHg, the subject will be treated according to the Clinical Investigator's discretion.
- AE assessments must be performed after each IVT injection.
- Upload collected images (SD-OCT) of the study eye to the central reading center.
- Schedule the subject to return for Visit 8 (Week 20 (D141±4)).

7.5.2.8. Visit 8 (Week 20 (D141±4))

- Perform the following assessments: (all ophthalmic procedures to be performed OU)
 - Query for AEs
 - Update medical history and medications
 - Vital signs
 - BCVA (ETDRS)
 - M-CHARTS™
 - Slit-lamp biomicroscopy
 - IOP
 - Indirect ophthalmoscopy
 - SD-OCT
 - SS-OCT angiography (for selected sites)
- Collect blood specimen for the following examinations:
 - PK serum sample (**for only the subjects who have consented under the protocol prior to Version 4.0**)
 - Biomarker serum sample
- **Perform Lucentis® administration** as per drug labeling, and then perform the following procedures after Lucentis® administration.
 - IOP will be measured at 40 (± 10) minutes post-injection.
 - If post-injection IOP is ≤ 21 mmHg AND increased < 10 mmHg from pre-injection IOP and there is no concern regarding retinal artery perfusion, DE-122 or Sham IVT will be administered.

- If post-injection IOP is > 21 mmHg OR increased ≥ 10 mmHg from pre-injection IOP, IOP measurement will be repeated at 60 (± 10) minutes post-injection.
- IOP will be measured at 60 (± 10) minutes post-injection, if applicable.
 - If post-injection IOP at 60 (± 10) minutes is ≤ 21 mmHg AND increased < 10 mmHg from pre-injection IOP and there is no concern regarding retinal artery perfusion, DE-122 or Sham IVT will be administered.
 - If post-injection IOP at 60 (± 10) minutes is > 21 mmHg, however the IOP is < 30 mmHg AND increased < 10 mmHg from pre-injection IOP and there is no concern regarding retinal artery perfusion, DE-122 or Sham IVT will be administered per the Clinical Investigator's discretion.
If the Clinical Investigator determine that DE-122 or Sham IVT will Not be administered, the subject will be treated according to the Clinical Investigator's discretion. The DE-122 or Sham IVT injection can be performed at the follow up visit (within the time window of Visit 8) per the Clinical Investigator's discretion.
 - **If post-injection IOP at 60 (± 10) minutes is ≥ 30 mmHg OR increased ≥ 10 mmHg from pre-injection IOP, DE-122 or Sham IVT should not be administered at the day of the visit.** Per the Clinical Investigator and Medical Monitor, the DE-122 or Sham IVT injection can be performed if IOP at the follow up visit (within the time window of Visit 8) is < 30 mmHg AND increased < 10 mmHg from pre-injection IOP and there is no concern regarding retinal artery perfusion.
If DE-122 or Sham IVT injection will not be performed, the subject should be prescribed a topical IOP-lowering medication until he or she returns for follow-up per the Clinical Investigator's discretion (an unscheduled visit may apply), and the event will be reported as an AE.
- **Perform DE-122 or Sham administration**, and then perform the following procedures after DE-122 or Sham administration.
- After DE-122 or Sham administration, the following will be performed: (all ophthalmic procedures to be performed OU)
 - Within 30 minutes following DE-122 or Sham IVT
 - Slit-lamp biomicroscopy
 - Indirect ophthalmoscopy
 - IOP measurement 40 (± 10) minutes following DE-122 or Sham IVT injection
 - If post-DE-122 or Sham injection IOP is > 21 mmHg OR increased ≥ 10 mmHg from pre-Lucentis[®] injection, IOP measurement will be repeated at 60 (± 10) minutes post-injection.
 - IOP will be measured at 60 (± 10) minutes following DE-122 or Sham IVT injection, if applicable.

- If post-DE-122 or Sham injection IOP at 60 (± 10) minutes is ≥ 30 mmHg OR increased ≥ 10 mmHg from pre-Lucentis[®] injection IOP, the subject should be prescribed a topical IOP-lowering medication, and the IOP elevation will be reported as an AE. Per the Clinical Investigator's discretion, the subject can return for follow-up (an unscheduled visit may apply).
- If post-DE-122 or Sham injection IOP at 60 (± 10) minutes is > 21 mmHg AND < 30 mmHg, the subject will be treated according to the Clinical Investigator's discretion.
- AE assessments must be performed after each IVT injection.
- If the subject has consented to Biomarker aqueous humor sample collection, collect the aqueous humor sample after DE-122 or Sham IVT.
- Collect blood specimen for the following examinations at 3 hrs (± 10 mins) post DE-122 or Sham injection. If DE-122 or Sham IVT injection is skipped, the blood sampling will be done at 3 hrs (± 10 mins) post Lucentis[®] administration:
 - PK serum sample (**for only the subjects who have consented under the protocol prior to Version 4.0**)
 - Biomarker serum sample
- Upload collected images (SD-OCT) of the study eye to the central reading center.
- Schedule the subject to return for Visit 9 (Week 20 + 2 days) or Visit 10 (Week 20 + 7 (± 1) days).

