7.5.2.4. Visit 4 (Week 4 (D29±3))

- Perform the following assessments: (all ophthalmic procedures to be performed OU)
 - Query for AEs
 - Update medical history and medications
 - Vital signs
 - BCVA (ETDRS)
 - M-CHARTS™
 - Slit-lamp biomicroscopy
 - IOP
 - Indirect ophthalmoscopy
 - SD-OCT
 - SS-OCT angiography (for selected sites)
 - Fundus photography
 - Fluorescein angiography
- Collect urine and blood specimen for the following examinations:
 - Urinalysis
 - Hematology, chemistry serum sample
 - PK serum sample (**for only the subjects who have consented under the protocol prior to Version 4.0**)
 - Biomarker serum sample
- **Perform Lucentis® administration** as per drug labeling, and then perform the following procedures after Lucentis® administration.
 - IOP will be measured at 40 (± 10) minutes post-injection.
 - If post-injection IOP is ≤ 21 mmHg AND increased < 10 mmHg from pre-injection IOP and there is no concern regarding retinal artery perfusion, DE-122 or Sham IVT will be administered.
 - If post-injection IOP is > 21 mmHg OR increased ≥ 10 mmHg from pre-injection IOP, IOP measurement will be repeated at 60 (± 10) minutes post-injection.
 - IOP will be measured at 60 (± 10) minutes post-injection, if applicable.
 - If post-injection IOP at 60 (± 10) minutes is ≤ 21 mmHg AND increased < 10 mmHg from pre-injection IOP and there is no concern regarding retinal artery perfusion, DE-122 or Sham IVT will be administered.

- If post-injection IOP at 60 (± 10) minutes is > 21 mmHg, however the IOP is < 30 mmHg AND increased < 10 mmHg from pre-injection IOP and there is no concern regarding retinal artery perfusion, DE-122 or Sham IVT will be administered per the Clinical Investigator's discretion.
If the Clinical Investigator determine that DE-122 or Sham IVT will Not be administered, the subject will be treated according to the Clinical Investigator's discretion.
- **If post-injection IOP at 60 (± 10) minutes is ≥ 30 mmHg OR increased ≥ 10 mmHg from pre-injection IOP, DE-122 or Sham IVT should not be administered.** The subject should be prescribed a topical IOP-lowering medication until he or she returns for follow-up per the Clinical Investigator's discretion (an unscheduled visit may apply), and the event will be reported as an AE.
- **Perform DE-122 or Sham administration**, and then perform the following procedures after DE-122 or Sham administration.

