23.4.8. Intraocular Pressure

IOP will be measured by applanation tonometry at each study visit except Visit 2 (Day 3), Visit 9 (Week 20 + 2 days) and Visit 10 (Week 20 + 7 days).

At visits with IVT injection, IOP will be measured before Lucentis® injection and 40 (± 10) minutes after injection. If post-Lucentis® injection IOP is > 21 mmHg or increased ≥ 10 mmHg from pre-injection IOP, the IOP measurement will be repeated at 60 (± 10) minutes following Lucentis® injection.

If post-injection IOP at 60 (± 10) minutes is ≥ 30 mmHg OR increased ≥ 10 mmHg from pre-injection IOP, the subject should be prescribed a topical IOP-lowering medication until he or she returns for follow-up per the Clinical Investigator's discretion, and the event will be reported as an AE.

IOP will be also measured after DE-122 or Sham injection. If post-DE-122 or Sham injection IOP is > 21 mmHg OR increased ≥ 10 mmHg from pre-Lucentis® injection at 40 (± 10) minutes after injection, the IOP measurement will be repeated at 60 (± 10) minutes after the injection. If post-DE-122 or Sham injection IOP at 60 (± 10) minutes is ≥ 30 mmHg OR increased

≥ 10 mmHg from pre-Lucentis® injection IOP, the subject should be prescribed a topical IOP-lowering medication, and the IOP elevation will be reported as an AE. If post-injection IOP at 60 (± 10) minutes is > 21 mmHg AND < 30 mmHg, the subject will be managed according to the Clinical Investigator's discretion.

If rescue IVT injection is performed, IOP will be measured 40 (± 10) minutes after the injection. If post-injection IOP is > 21 mmHg OR increased ≥ 10 mmHg from pre-injection IOP, IOP measurement will be repeated at 60 (± 10) minutes post-injection. If post-injection IOP at 60 (± 10) minutes is ≥ 30 mmHg OR increased ≥ 10 mmHg from pre-injection IOP, the subject should be prescribed a topical IOP-lowering medication, and the IOP elevation will be reported as an AE. Per the Clinical Investigator's discretion, the subject can return for follow-up. If post-injection IOP at 60 (± 10) minutes is > 21 mmHg AND < 30 mmHg, the subject will be managed according to the Clinical Investigator's discretion.

The applanation tonometer must be calibrated for accuracy before the first subject undergoes screening, and periodically until the last subject has exited the study. For checking calibration, follow the manufacturer's instructions.

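### Week 20 ties the action and AE report for a post-Lucentis IOP spike to DE-122/Sham not being performed, unlike the rest of the protocol, and the paired post-injection IOP bullets overlap at every injection and rescue visit

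*Protocol*

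**What the plan says.** **After Lucentis, Week 20.** Protocol 7.5.2.8 bars same-day DE-122/Sham if the 60-minute IOP is 30 mmHg or more or has risen by 10 mmHg or more. Subject to the investigator and the Medical Monitor, "the DE-122 or Sham IVT injection can be performed if IOP at the follow up visit (within the time window of Visit 8") meets stated limits. The text continues: "If DE-122 or Sham IVT injection will not be performed, the subject should be prescribed a topical IOP-lowering medication" until follow-up, with the event reported as an AE.

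**After Lucentis, elsewhere.** For the same reading, Protocol 7.5.2.7 (Week 16) says "The subject should be prescribed a topical IOP-lowering medication until he or she returns for follow-up per the Clinical Investigator's discretion" and requires an AE report, with no condition. Visits 1, 4, 5 and 6 (7.5.2.1, 7.5.2.4 to 7.5.2.6) do the same. Appendix D 23.4.8 states its scope as "At visits with IVT injection, IOP will be measured before Lucentis® injection", so Week 20 is included. It requires that "the subject should be prescribed a topical IOP-lowering medication until he or she returns for follow-up per the Clinical Investigator's discretion", and the AE report as well, whether or not DE-122/Sham follows.

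**AE criterion.** Protocol 12.2.6 and SAP Table 5 make a 60-minute rise of 10 mmHg or more an AE. Neither includes the 30 mmHg threshold.

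**After DE-122/Sham or rescue.** One 60-minute bullet requires topical medication and an AE report for 30 mmHg or more, or a rise of 10 mmHg or more. The next covers IOP "> 21 mmHg AND < 30 mmHg, the subject will be treated according to the Clinical Investigator's discretion", with no limit on the size of the rise.

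**The concern.** Safety is part of the primary objective, and SAP 9.1 tabulates AEs by treatment received. An IOP elevation should therefore lead to the same AE record at every injection visit. On one reading of the Week 20 sentence, an eye whose injection is deferred and then given falls outside both the medication instruction and the AE instruction in that section, although the same reading triggers both at the other five injection visits and under Appendix D.

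The overlapping bullets raise a separate problem: for one reading a site has two instructions on medication, one mandatory and one discretionary. DE-122 adds 20 or 40 µL to the eye, while sham does not penetrate it. If rises are more common after a true injection, inconsistent handling between sites would not fall equally on the arms.

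**Working it through.** No sample-size, power or alpha figure is involved. The check sets the rules side by side and enumerates whole-mmHg readings.

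**1. Post-Lucentis spike (30 mmHg or more, or a rise of 10 or more, at 60 minutes)**

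| Source | Medication | AE report |
|---|---|---|
| Visits 1, 4, 5, 6, 7 | required | required |
| Appendix D 23.4.8 (all visits with an injection) | required | required |
| Visit 8, 7.5.2.8 | if DE-122/Sham is not to be performed | same condition |
| Protocol 12.2.6, SAP Table 5 | not stated | required for a rise of 10 or more |

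The Visit 8 window is D141±4, that is Day 141 − 4 = 137 to Day 141 + 4 = 145. A deferral can last at most 145 − 137 = 8 days.

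**2. Spikes outside the rise-based AE rule**

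A reading of 30 or more with a rise below 10 needs a pre-injection IOP p with 30 − p < 10, so p > 20. For whole numbers the readings run from 30 to p + 9. At p = 21 the only one is 30. If p were 25 at a later visit (assumption), they would be 30 to 34. These fall outside 12.2.6, SAP Table 5 and the SAP 9.4 listing; at Week 20 only 23.4.8 makes them an AE unconditionally.

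**3. Overlap of the paired bullets after DE-122/Sham or rescue**

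Let p be the reference pre-injection IOP (pre-Lucentis for DE-122/Sham) and x the 60-minute IOP.

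- Bullet A (medication and AE): x ≥ 30 or x − p ≥ 10.
- Bullet B (discretion): 21 < x < 30.
- Both apply when x > 21, x ≥ p + 10 and x < 30. This is possible only if p + 10 < 30, so p < 20.

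I took p from 6 to 21 mmHg, an assumed range based on the limits in exclusion criterion 2.

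| p (mmHg) | x under both bullets | Number of readings |
|---|---|---|
| 6 to 12 | 22–29 | 7 × 8 = 56 |
| 13 | 23–29 | 7 |
| 14 | 24–29 | 6 |
| 15 | 25–29 | 5 |
| 16 | 26–29 | 4 |
| 17 | 27–29 | 3 |
| 18 | 28–29 | 2 |
| 19 | 29 | 1 |
| 20, 21 | none | 0 |

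Total: 56 + 28 = 84 pairs. Example: 14 to 25 mmHg is a rise of 11, so A applies; 25 lies between 21 and 30, so B applies.

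**4. Comparison with the post-Lucentis bullets**

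Their discretion band is limited to rises below 10 mmHg. With p from 6 to 21 and x from 6 to 45 (16 × 40 = 640 pairs), none falls under two bullets and none under no bullet, leaving the retinal-perfusion clause aside.

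**5. Where the overlapping pair occurs**

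All six injection visits (1 and 4 to 8), both rescue visits (11 and 12) and Appendix D 23.4.8: 6 + 2 = 8 visits plus the appendix.

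**The case against.** The best reply is that the rule is not missing. Appendix D requires medication and an AE report at Week 20 regardless of later dosing, and 12.2.6 and SAP Table 5 make a rise of 10 mmHg or more an AE. Section 7.5.2.8 requires AE assessment after each injection, which includes Lucentis. SAP 9.4 lists 60-minute rises of 10 mmHg or more from the IOP data, whether or not an AE was entered. All of this stands. The fault is a conflict between passages.

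Second, the Week 20 condition can be read as referring to that day only. When the spike is found, nobody knows whether a deferred injection will be given, and the medication is meant to bridge to the follow-up visit. This is a fair reading. But the sentence barring injection limits itself to the day of the visit, and the conditional sentence, coming after the deferral option, does not. A site could read it either way.

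Third, the discretion bullet concerns treatment and does not cancel the AE report required by the bullet before it. This also stands: the overlap is about medication, not AE counts.

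A reader might infer that spikes go untreated or uncounted, or that the IOP AE count is understated. The documents do not support that. For a rise of 10 mmHg or more, an AE would be missed only if a site followed the narrow reading of one sentence and disregarded both 12.2.6 and 23.4.8.

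**Conclusion.** Two internal conflicts hold.

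- **Week 20.** At one of six injection visits, the action and AE report for a post-Lucentis spike carry a condition found nowhere else. Events may be recorded or handled inconsistently when DE-122/Sham is deferred. The weakest cover is for a reading of 30 mmHg or more with a rise below 10 mmHg, where 23.4.8 alone applies unconditionally.
- **Paired bullets.** At all six injection visits, both rescue visits and in Appendix D, readings above 21 and below 30 mmHg with a rise of 10 mmHg or more carry two instructions on medication. The AE requirement is unaffected.

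The overlap follows from the stated thresholds; only the count of 84 pairs depends on the assumed range of 6 to 21 mmHg and on whole-number readings. It counts combinations, not patients. The documents give no rate of spikes or of deferred injections, so no number of affected events can be derived. This calls for clarification of safety instructions; it does not show that AE results are biased.

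**What to change.** Issue a protocol clarification letter and site note, with a matching SAP edit:

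1. In 7.5.2.8, state that AE recording of a qualifying 60-minute post-Lucentis IOP does not depend on whether DE-122/Sham is later given, consistent with 23.4.8.
2. Reconcile the AE criterion in 12.2.6 and SAP Table 5 (rise only) with 23.4.8 (rise or 30 mmHg).
3. Reconcile the Week 20 clinical action with the other injection visits and 23.4.8.
4. Reconcile the paired 60-minute bullets everywhere they occur, so that each reading leads to one instruction. Aligning Week 20 with 7.5.2.7 or 23.4.8 would not do this, because both contain the same overlap.

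The sponsor's medical lead decides which clinical rule applies in items 3 and 4; this review takes no view. The cost is the letter, the site note and the SAP edit, with no new procedures or data collection.
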